### 7.6.1 Adverse events

Pretreatment AEs are those occurring between ICF signature and the first IMP administration. Treatment-emergent Adverse Events (TEAEs) are defined as those AEs that start on or after the first dose of IMP and up to 8 weeks after the last dose of study medication.

An overall summary table will summarize the following information by treatment group.

- Treatment-emergent adverse events (TEAEs)
- Serious adverse events (SAEs)
- Non-serious adverse events
- TEAEs leading to premature discontinuation of IMP.
- TEAEs leading to death
- Device related TEAEs
- TEAEs by severity

Separate tables will be presented with the following summaries:

- TEAEs of special interest will be summarized: infections (defined as any AE with SOC “Infections and Infestations”), and injection site reactions (from eCRF)
- Pretreatment AEs by PT
- TEAEs by SOC and PT, including incidence rates.
- TEAEs by PT, including incidence rates.
- Non-serious TEAEs by SOC and PT, including incidence rates.
- Non-serious TEAEs PT, including incidence rates.
- Treatment-emergent SAEs PT, including incidence rates.
- TEAEs leading to premature discontinuation of IMP by PT, including incidence rates.
- TEAEs related to the IMP by PT, including incidence rates.
- Treatment-emergent SAEs related to the IMP by PT, including incidence rates.
- TEAEs by severity (mild/moderate/severe) and PT, including incidence rates.
- TEAEs that were injection site reactions, by PT.

The time at risk per patient is defined as time from first dose of study drug to last dose of study drug + 56 days (treatment-emergent), or death, if earlier, for those patients without a respective TEAE. For patients with an TEAE, time at risk is defined as the time from first dose of study drug to TEAE start date. Exposure adjusted incidence rates will be calculated as (number of patients with AE/total person-years at risk)\*100.

All AE data will be presented in a listing and include at least onset date, duration, relationship to IMP, severity, action taken with IMP, treatment of event, and outcome.

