6.5.4 Safety assessments

6.5.4.1 Adverse events

6.5.4.1.1 Definitions

Adverse event

An AE is any untoward medical occurrence in a patient or study subject during the course of the study (after signing of the informed consent), whether or not considered by the investigator as related to study treatment.

AEs include the following:

- Abnormal test findings, as specified below.
- Changes in physical examination findings.
- Progression/worsening of underlying disease.
- Signs and symptoms resulting from overdose, withdrawal of treatment, drug-drug interactions, abuse and misuse.
- Increase in frequency or intensity of a preexisting episodic disease or medical condition.
- Disease or medical condition detected or diagnosed during the course of the study even though it may have been present prior to the start of the study.
- Continuous persistent disease or symptoms present at study start that worsen following the start of the study.

For pregnancies and breastfeeding, see Section 6.5.4.1.5.

Abnormal test findings

An abnormal test finding, e.g. abnormal laboratory analysis results, vital signs or ECG, should be recorded as an AE in any of the following situations:

- The investigator considers the abnormal test finding to be clinically significant.
- The abnormal test finding leads to a medical/surgical intervention including withdrawal of IMP(s) or discontinuation from the study. Repeat/confirmatory testing is not considered a medical intervention.

Preexisting conditions

A preexisting condition (i.e., a disorder present before the AE reporting period started and noted on the pretreatment medical history/physical examination form) should not be reported as an AE unless the condition worsens or episodes increase in frequency during the AE reporting period.

AEs diagnosis versus signs/symptoms

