For any AE, a diagnosis should be recorded rather than individual signs and symptoms or abnormal laboratory findings. However, if at the time of AE reporting a diagnosis is not available, each individual sign/symptom should be recorded. If a diagnosis is subsequently established, all previously reported AEs based on signs and symptoms should be removed and replaced by one AE report based on the single diagnosis, with a starting date that corresponds to the start date of the first symptom of the eventual diagnosis. This approach also applies to signs and symptoms of CAD worsening, which should be reported as “CAD worsening/progression” or similar (e.g., relapse, flare progression or exacerbation), as appropriate.

Procedures

Diagnostic and therapeutic noninvasive and invasive procedures, such as surgery, should not be reported as AEs. However, the medical condition for which the procedure was performed should be reported if it meets the definition of an AE. For example, an acute appendicitis that begins during the AE reporting period should be reported as the AE and the resulting appendectomy entered in the comments section of the eCRF.

Treatment-emergent adverse event

A treatment-emergent AE is any AE temporally associated with the use of study treatment, i.e., from study treatment initiation until 8 weeks after study treatment discontinuation.

Serious adverse event

An AE that meets one or more of the following criteria/outcomes is classified as serious:

- Results in death.
- Is life threatening (i.e., at immediate risk of death).
- Requires in-patient hospitalization or prolongation of existing hospitalization.
- Results in persistent or significant disability/incapacity.
- Is a congenital anomaly/birth defect (i.e., in an offspring to the study patient).
- Is a medically important AE.

Medically important AEs are events that may not result in death, be life threatening, or require hospitalization but may be considered serious when, based upon appropriate medical judgment, may jeopardize the patient or subject or may require medical or surgical intervention to prevent one of the outcomes listed above. Examples of such events are intensive treatment in an emergency room or at home for allergic bronchospasm, blood dyscrasias or convulsions that do not result in hospitalization or development of dependency or abuse.

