6.5.4.1.3 Obtaining and recording adverse event information

The investigator obtains AE information that is directly observed or solicited from the patient or patient relative during the course of the study. All AEs must be recorded in the eCRF using concise medical terminology.

The investigator is responsible for obtaining sufficient information to determine seriousness, causality and outcome of each AE.

Severity assessment

The investigator will use the adjectives MILD, MODERATE, or SEVERE to describe the maximum severity of the AE. For the purpose of consistency, these severity grades are defined as follows:

MILD	Does not interfere with patient's usual function
MODERATE	Interferes to some extent with patient's usual function
SEVERE	Interferes significantly with patient's usual function

Note the distinction between the gravity (seriousness) and the severity of an AE. **Severe** is a measure of intensity; thus, a **severe** event is not necessarily a **serious** event. For example, a headache may be severe in intensity, but would not be classified as serious unless it met one of the criteria for serious events listed above.

Causality assessment

For each AE, the investigator must make a causality assessment to determine if there is a reasonable possibility that the IMP(s) caused the AE. The AE is assessed as **related** or **not related** to the IMP(s).

6.5.4.1.3.1 Reporting of adverse event to an auxiliary medicinal product

All AEs occurring after initiation of AxMP should also be reported in line with the reporting requirements stated above. Relationship to AxMP should be stated.

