8.3.5 Analysis of safety and tolerability data

All safety analyses will be carried out descriptively on the safety set, consisting of all patients who received at least 1 dose of IMP.

In general, the evaluation of safety and tolerability is carried out separately for the double-blind placebo-controlled period and the open-label period. Other analyses are detailed in the SAP.

Pretreatment AEs are those occurring between ICF signature and the first IMP administration. TEAEs are defined as those AEs that develop or worsen after the first dose of IMP and up to 8 weeks after the last dose of study medication.

All AEs will be coded using the MedDRA. Pretreatment AEs will be summarized by SOC and PT. TEAEs will be summarized by SOC, PT, treatment group for number of patients and proportion reporting the event. A similar summary will be produced for SAEs, AEs leading to premature discontinuation of IMP and AEs related to the IMP. The intensity of AEs and the relationship to the IMP will be summarized for each SOC and PT by treatment group.

AEs leading to IMP discontinuation will be summarized by frequency tables.

The results of laboratory assessments, anti-pegcetacoplan peptide/anti-PEG Ab assessments, vital signs and ECGs will be summarized by treatment group using appropriate descriptive statistics.

The AE summaries will be presented across all patients. All AEs will be listed by patient, along with information regarding onset, duration, relationship to IMP, severity, action taken with IMP, treatment of event and outcome.

Changes from Baseline in clinical laboratory test results will be summarized using descriptive statistics. Baseline will be taken as the measurement closest, but prior, to the first dose of IMP. Out-of-range values will be flagged in data listings.

Laboratory data and vital signs will be graded for severity using CTCAE v 5.0 and all Grade ≥ 3 results will be considered clinically meaningful.

Changes in physical examinations will be described in a data listing.

Safety data will include all data up to Week 24 for reporting Part A, all data up to Week 48 for reporting Part B, and all data for reporting Part C.

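### SAP 7.6.1 defines treatment-emergent AEs by start date alone and drops the protocol's worsening limb without saying so, so a pre-dose AE record that worsens on study drug leaves the TEAE tables

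*SAP*

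**What the plan says.** Protocol 8.3.5, the protocol's section on safety analysis, states: "TEAEs are defined as those AEs that develop or worsen after the first dose of IMP", with a window that closes 8 weeks after the final dose. SAP 7.6.1 closes the window at the same point but states: "Treatment-emergent Adverse Events (TEAEs) are defined as those AEs that start on or after the first dose of IMP". It also states: "Pretreatment AEs are those occurring between ICF signature and the first IMP administration".

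Protocol 6.5.4.1.1 gives a second, looser description: "A treatment-emergent AE is any AE temporally associated with the use of study treatment", running from the start of treatment to 8 weeks after it stops. That section also lists, among the things that are AEs, "Continuous persistent disease or symptoms present at study start that worsen following the start of the study".

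Two recording rules matter here. Under protocol 6.5.4.1.1, a later diagnosis replaces the symptom records with one AE, "with a starting date that corresponds to the start date of the first symptom of the eventual diagnosis", and this explicitly extends to worsening of CAD. Under protocol 6.5.4.1.3, the investigator grades each event "to describe the maximum severity of the AE".

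SAP 11.1, headed as changes to the protocol's analyses, lists none and says only that the SAP prevails where the two differ. SAP 1.1 keeps the safety summaries in full despite the early stop of enrollment.

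**The concern.** The SAP rule looks only at when an AE record begins. The protocol's analysis rule also counts an event that began earlier and became worse once treatment started. Where a pre-dose event is kept as one record, with its original start date and its worst grade, the deterioration on study drug is attached to a date that the SAP treats as pretreatment.

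At stake are the TEAE tables, the related-TEAE and treatment-emergent SAE tables, the infections-of-special-interest table and the exposure-adjusted rates. Relative to the protocol definition, the SAP definition can only remove events and never adds any. An unannounced narrowing of the core safety definition, in the direction of fewer reported events, should not rest on a general precedence clause.

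**Working it through.** No power or sample size calculation is involved. The check compares texts, with one percentage and one time-at-risk calculation.

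**1. The two definitions**
- Protocol 8.3.5: starts or worsens after the first dose, window to 8 weeks after the last dose.
- SAP 7.6.1: starts on or after the first dose, same window (its time-at-risk rule uses 56 days, and 8 × 7 = 56).
- Apart from the trivial wording of after versus on-or-after, the difference is the worsening limb.

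**2. Does other SAP text restore worsening?** No. The only exception to the start-date rule is in SAP 5.2.2, where an AE with no start date counts as treatment-emergent. It does not deal with worsening.

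**3. Which records can be affected?**
- Before dosing the protocol collects SAEs (6.5.4.1.2; Table 1 marks only SAEs at screening) and AEs after an auxiliary product, here the screening vaccines (6.4.1.2.1, 6.5.4.1.3.1).
- A diagnosis made after dosing can acquire a pre-dose start through the back-dating rule in 6.5.4.1.1.
- A medical-history condition that worsens is itself reported as an AE (6.5.1, 6.5.4.1.1; similarly 6.5.4.6 and 6.5.4.7). If it is entered with its own onset after dosing, it is a TEAE under either definition.
- For an AE already open at first dose, protocol 6.5.4.1.6 leaves the recording of changes to the eCRF instructions, which are not among the documents. Whether worsening opens a new record is therefore unknown.

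**4. What happens to a single record that starts before dosing and worsens after it?** It meets protocol 8.3.5 and fails SAP 7.6.1. If it began after consent, it is a pretreatment AE; if back-dating puts it before consent, it falls in neither SAP class. In both cases it stays in the listing of all AEs.

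**5. Size per patient**
- Planned pegcetacoplan patients: 57 × 2/3 = 38. One patient: 1/38 = 2.6 percentage points.
- This is a maximum for one table row. If the patient has another qualifying event in that row, the percentage does not change.

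**6. Effect on exposure-adjusted rates.** SAP 7.6.1 runs time at risk from first dose to TEAE start for patients with the event, and to last dose + 56 days (or death) for those without. Dropping an affected patient from a row with no other event lowers the numerator by 1 and lengthens the denominator, so the rate falls. Conversely, if worsening is restored without changing the event date, an AE that began *k* days before first dose contributes roughly −*k* days at risk. The date of worsening has to be used.

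**The case against.** The strongest case against is that the AE collection rules already deal with most of this. Non-serious AEs are generally recorded only from the first dose, worsening of a concomitant illness is an AE in its own right, and the eCRF instructions may require a new record when an ongoing AE worsens. Protocol 6.5.4.1.1 also has a TEAE description without a worsening limb, with which the SAP wording is compatible. Affected events are not hidden: SAP 7.6.1 plans a pretreatment AE table, an overall SAE row not labelled treatment-emergent, and a full listing.

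Much of this stands. It makes the affected pool narrow and the loss one of tabulation rather than of reporting. It does not remove the conflict with protocol 8.3.5, which is the protocol's analysis rule, and neither document guarantees a new record on worsening.

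Three stronger readings are tempting, and the documents do not support them:

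- A reader might infer that every event diagnosed on drug after a pre-dose symptom is lost because the worsening limb was dropped. An event that was only diagnosed on drug, without worsening, would not clearly be a TEAE under protocol 8.3.5 either. That effect comes from the protocol's own back-dating rule.
- A reader might infer that serious encapsulated infections are likely to vanish from the tables. Protocol 4.3 calls these a potential increased risk and reports no meningococcal or other severe infection potentially related to encapsulated bacteria. Exclusion criteria 15, 16 and 22 remove some infections present before dosing. Events that straddle the first dose are plausible; nothing shows that they are to be expected.
- A reader might want a larger percentage per patient because enrollment stopped early. The direction is right, but SAP 1.1 does not say how many patients were randomized, so no such figure can be given.

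**Conclusion.** The discrepancy is real, undocumented and still in force. It excludes from the TEAE tables and rates any AE that has a pre-dose start, worsens on IMP and is kept as one record. Relative to protocol 8.3.5, the effect can only lower the counts.

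The number of such events cannot be derived from the documents and is probably small. The bound of 2.6 points per patient in a given category assumes the planned 38 pegcetacoplan patients and no other qualifying event for that patient in the category. The conclusion also assumes that the eCRF instructions do not force a new record when an AE worsens; if they do, what remains is mainly the back-dated diagnoses. The point is worth correcting because it touches the core safety definition and costs almost nothing, not because a large distortion has been shown.

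**What to change.** 1. In SAP 7.6.1, define a TEAE as an AE that starts or worsens on or after the first IMP dose and no later than 8 weeks after the last. If the narrower rule is intended, list it in SAP 11.1 with a reason.
2. Identify AEs with a pre-dose start that were ongoing at first dose, including diagnoses back-dated under protocol 6.5.4.1.1, and classify each by whether it worsened after first dose. Do this at the blinded data review that SAP 4.4 and 6.6 already plan. That meeting is described there for per-protocol decisions, which SAP 1.1 has since dropped, so the SAP should confirm that it will still take place or name another blinded review before database lock.
3. Where the date of worsening is unknown, count the event as treatment-emergent, in line with how SAP 5.2.2 treats a missing start date.
4. For events that qualify through worsening, use the date of worsening as the event date for time at risk.

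The cost is a few sentences in the SAP and a review of a handful of records. The downside is that TEAE counts may rise slightly.

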### **7.6.2 Laboratory data**

Laboratory data will be graded for severity using the CTCAE v5.0 and all results of grade  $\geq 3$  will be considered clinically meaningful.

A frequency table will be presented to summarize patients with CTCAE grading  $\geq 3$  from Baseline until 8 weeks after end of treatment for each laboratory parameter for hematology, chemistry, and urinalysis.

Concentrations below the lower limit of quantification (LLOQ) (e.g., <0.20) or upper limit of quantification (ULOQ) will be replaced with LLOQ (e.g., 0.20) or ULOQ in summary tables. In listings, the original value will be presented (e.g., “BLQ” or “<0.20”). When an imputation is made in a summary table, a footnote will be added with the imputation approach.

A summary table will be presented with descriptive statistics and change from baseline for all laboratory parameters. Baseline will be taken as the last measurement prior to the first dose of IMP. For urinalysis parameters that are categorical (e.g., “None”, “Trace”, “1+”), a categorical summary of urinalysis results may be created to complement quantitative results.

All laboratory data will be presented in a listing and values outside normal range values will be flagged.

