6.3 Selection of study population

6.3.1 Inclusion criteria

A patient must fulfill the following criteria to be included in the study:

1. Age 18 years or older.
2. Diagnosis of primary CAD on the basis of the presence of all the following criteria at screening:
 - a. Signs of hemolysis with abnormal values for at least 2 of the following hemolytic markers:
 - i. Reduced haptoglobin level (< LLN).
 - ii. Elevated LDH level (> ULN).
 - iii. Elevated indirect bilirubin level (> ULN; > 3 x ULN for patients with Gilbert-Meilengracht syndrome).

iv. Increased ARC (above the ULN).

- b. Monospecific direct antiglobulin test strongly positive for C3d.
- c. Cold agglutinin titer ≥ 64 at 4°C .

3. Hb level ≤ 9 g/dL at screening.
4. An absolute neutrophil count ≥ 1500 cells/mm 3 at screening.
5. Documented results from bone marrow biopsy within 1 year of screening with lymphoproliferative infiltration $\leq 20\%$. Patients who have not received a bone marrow biopsy within 1 year of their screening visit or for whom bone marrow biopsy reports are incomplete or unavailable will be required to receive a bone marrow biopsy to determine eligibility.
6. Body weight ≤ 100 kg.
7. Either have vaccination against *S. pneumoniae*, *N. meningitidis* (Types A, C, W, Y, and B), and *H. influenzae* (Type B) within 2 years prior to screening or agree to receive vaccination during screening as follows:
 - First dose of vaccine against *N. meningitidis* Types A, C, W, and Y at least 2 weeks prior to start of study drug with second dose 2 months later (Study Day 57), and then boosters every 5 years.
 - First dose of the vaccine against *N. meningitidis* Type B at least 2 weeks prior to start of study drug with a second dose after at least 1 month (Study Day 29). First booster dose 1 year later, and then additional booster doses every 2 to 3 years.
 - *S. pneumoniae*: PCV13 and/or PPSV23 as per ACIP guidelines for adults or children with immunocompromising conditions.
 - *H. influenzae* Type B: 1 dose at least 2 weeks prior to start of study drug.

Vaccination is mandatory unless documented evidence exists that patients are nonresponders to vaccination. Vaccinations should be administered following the ACIP recommendations for adults or children with complement deficiencies and/or immunocompromising conditions.

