### **7.6.4 Vital sign data**

Vital signs will be graded for severity using the CTCAE v5.0 and all results of grade  $\geq 3$  will be considered clinically meaningful. A frequency table will be presented to summarize the clinically meaningful abnormalities as recorded from treatment start date until 8 weeks after end of treatment for each parameter.

A summary table will be presented with descriptive statistics and change from baseline for all parameters.

All vital sign data including the overall interpretation (normal and if abnormal CS/NCS, Not Evaluable / Not done, etc.) as assessed by the will be presented in a listing. Reference ranges for heart rate, respiratory rate, blood pressure and body temperature will be added and values will be flagged as High/Low according to the reference ranges.

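### The Grade 3-or-higher laboratory table in SAP 7.6.2 opens at a pre-dose Baseline and has no worsening rule, so it can count disease values that were present before treatment

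*SAP*

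**What the plan says.** The protocol's safety endpoints (5.2.1.4) include clinically meaningful laboratory abnormalities up to 8 weeks after end of treatment. Protocol 8.3.5 defines the term: "Laboratory data and vital signs will be graded for severity using CTCAE v 5.0 and all Grade ≥ 3 results will be considered clinically meaningful". SAP 7.6.2 adopts the same threshold and plans a frequency table of patients reaching it "from Baseline until 8 weeks after end of treatment for each laboratory parameter for hematology, chemistry, and urinalysis". The same section states that "Baseline will be taken as the last measurement prior to the first dose of IMP", which agrees with SAP 5.2.1.

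Neither SAP 7.6.2 nor protocol 8.3.5 compares the grade with the baseline grade, and no shift table is planned in SAP 7.6. For vital signs, which have the same Grade 3 threshold, SAP 7.6.4 counts abnormalities "as recorded from treatment start date until 8 weeks after end of treatment for each parameter".

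Entry requires "Hb level ≤ 9 g/dL at screening" (protocol 6.3.1), with no lower limit, and at least two hemolysis markers outside normal limits. SAP 1.1 cuts the efficacy analyses after early termination but keeps the safety summaries, so this table will be produced.

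**The concern.** A safety table of severe laboratory values should show what happened on treatment. This one opens on an untreated value in patients selected for anemia. Any patient whose baseline hemoglobin is already Grade 3 or higher is counted before receiving drug or placebo. Reading the window as post-baseline only does not remove the problem. Without a worsening rule, a Grade 3 value that is still present at Week 1 counts even if it is improving.

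At stake is how a named safety endpoint is read. For hemoglobin the table would mix entry disease with on-treatment events. The reported rate would be too high in both arms, the relative contrast between arms would be flattened, and a patient who is improving could be shown as having a clinically meaningful abnormality.

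A lesser question is whether the table covers coagulation, which is not among the panels it names.

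**Working it through.** The documents state no figure that depends on this rule, so there is none to reproduce. The check sets the rules side by side and then works out the direction of the effect.

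**Counting rules**

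- Laboratory table (SAP 7.6.2): opens at Baseline, a pre-dose value; no worsening condition.
- Vital-sign table (SAP 7.6.4): opens at the start of treatment; no worsening condition.
- Treatment-emergent adverse events: onset on or after the first dose (SAP 7.6.1); protocol 8.3.5 speaks of events that develop or worsen after it.
- Preexisting conditions (protocol 6.5.4.1.1): not adverse events unless they worsen or become more frequent.

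Of these, only the laboratory table opens before treatment, and no reason is given.

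**Can Grade 3 or higher values be present at entry?** The hemoglobin criterion is a ceiling. Protocol 6.1.1 allows transfusion for acute hemolytic crisis during screening, and 6.1.2 has a transfusion rule for hemoglobin below 7.0 g/dL in Part A. Very low values are therefore foreseen. The documents do not give the CTCAE cut-offs or the share of patients beyond them.

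**Effect on the table.** Let q be the share of each arm at Grade 3 or higher at Baseline, and r the risk of a new Grade 3 or higher result in the rest. Assume for simplicity that q is the same in both arms and that no patient already at Grade 3 or higher moves to a still higher grade. The denominator is the SAP default (9.2.5.2): patients in the analysis set with an observation.

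- SAP rule: q + (1 − q)r
- New-or-worsened rule: (1 − q)r
- Increase caused by the SAP rule: q in each arm
- Difference between arms under either rule: (1 − q)(r₁ − r₀)

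Illustration with assumed q = 40% and r = 5% versus 30%:

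- SAP rule: 0.40 + 0.60 × 0.05 = 43%; 0.40 + 0.60 × 0.30 = 58%. Difference 15 points, ratio 58/43 = 1.35.
- New-or-worsened rule: 0.60 × 0.05 = 3%; 0.60 × 0.30 = 18%. Difference 15 points, ratio 18/3 = 6.0.

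A second illustration, with assumed r = 15% versus 5%, over a range of q:

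| q | SAP rule | New-or-worsened rule | Difference, both rules | Ratio, SAP rule | Ratio, new-or-worsened rule |
|---|---|---|---|---|---|
| 0% | 15.0% vs 5.0% | 15.0% vs 5.0% | 10 points | 3.0 | 3.0 |
| 10% | 23.5% vs 14.5% | 13.5% vs 4.5% | 9 points | 1.62 | 3.0 |
| 30% | 40.5% vs 33.5% | 10.5% vs 3.5% | 7 points | 1.21 | 3.0 |
| 50% | 57.5% vs 52.5% | 7.5% vs 2.5% | 5 points | 1.10 | 3.0 |
| 70% | 74.5% vs 71.5% | 4.5% vs 1.5% | 3 points | 1.04 | 3.0 |

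The difference falls down the rows because fewer patients are at risk of a new abnormality. Within each row both rules give the same difference.

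**Coagulation.** Protocol Table 4 lists it as a panel separate from hematology, and Table 1 schedules it at every post-dose visit in Part A. Protocol 4.3, however, describes hematology as including coagulation. The three panels named in SAP 7.6.2 can be read either way.

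**The case against.** The strongest reply is that little rests on this table. Safety analysis is descriptive. SAP 7.6.2 also plans a change-from-baseline summary for all laboratory parameters and a listing with out-of-range values flagged. For hemoglobin, change from Baseline is a key secondary endpoint with its own model. The Grade 3 threshold comes from the protocol. Baseline assessments are planned for Day 1 or the day before (protocol 6.5.3), so the window's label may simply mean the on-treatment period. The endpoint list in 5.2.1.4 mentions Baseline for vital signs too, where SAP 7.6.4 uses the start of treatment.

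Most of this stands as mitigation. It keeps the point modest, but it does not supply a worsening rule under either reading of the window. Mean changes and listings also do not replace the only frequency table planned for this endpoint.

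A reader might infer three stronger things that the documents do not support:

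- **That the anemia and hemolysis required at entry are themselves reported as severe abnormalities.** Entry requires hemoglobin at or below a ceiling and markers outside normal limits, not Grade 3. Only values that actually reach Grade 3 are counted. The case is clearest for hemoglobin and less certain for the hemolysis markers.
- **That the rule shrinks the absolute difference, for example from 25 points to 15.** That comparison sets a rate among all patients (43% versus 58%) against a rate among only those below Grade 3 at entry (5% versus 30%). On one denominator the difference is 15 points under both rules.
- **That coagulation is left out of the analysis.** At most it is missing from this one frequency table. The all-parameter summary and the listing cover it, and protocol 4.3 allows a reading in which hematology includes it.

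**Conclusion.** The point holds as a defect in one safety table. As written, SAP 7.6.2 can count Grade 3 or higher values, chiefly low hemoglobin, that were present before the first dose or only persist after it. When the baseline value counts, each arm's reported rate rises by its share at Grade 3 or higher at entry. The ratio between arms moves toward 1, and the absolute difference on the full denominator does not change.

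The size cannot be fixed from the documents. It is zero if nobody enters at Grade 3 or higher and grows with that share; every percentage above is an assumption. The equal-difference result also assumes the same entry share in both arms and no differential movement to a still higher grade. In a small trial whose enrollment stopped early, chance imbalance in the entry share would pass directly into the reported difference. If the window is read as post-baseline only, the amount added is the share whose Grade 3 or higher value persists to some post-dose visit, which treatment could make unequal between arms.

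No test or efficacy conclusion depends on this table. Coagulation is an ambiguity to settle, not a demonstrated omission.

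**What to change.** In SAP 7.6.2:

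1. Start the window at the first dose, as SAP 7.6.4 does for vital signs.
2. Count a patient only for a post-dose result that is Grade 3 or higher and of a higher grade than at Baseline.
3. Add a shift table of baseline grade by worst post-baseline grade.
4. Name coagulation among the panels, which settles the difference between protocol 4.3 and Table 4.

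The cost is a few lines of SAP wording and one extra table; no new data are needed. The drawback is that a patient already at the highest grade at Baseline cannot count as worsening. The shift table makes those patients visible.
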